### 13.3 Inspecting

The investigator must be aware that a regulatory authority(ies) may be conducting an official review of documents, facilities, records, and other resources that are deemed by the authority(ies) to be related to the clinical study. Participation as an investigator in this study implies acceptance of potential inspection by government regulatory authorities and applicable

quality assurance offices. The Principle Investigator is responsible for informing the sponsor of an inspection as soon as he/she becomes aware of it.

## **14 STUDY FINANCES**

### **14.1 Funding**

The sponsor will provide a research grant for the study. A budget will be developed with the investigator and all financial aspects of the study will be documented in a separate agreement between the sponsor and the investigator/institution.

### **14.2 Insurance**

The sponsor maintains a program of comprehensive general liability insurance and product liability insurance for the duration of the study at levels sufficient to support the indemnification obligations assumed under the separate agreement “Investigator Agreement – Study No. CAN-PRO-NEPA-001 Responsibilities and Procedures”.

The investigator also maintains a program of comprehensive general liability insurance for the duration of the study at levels sufficient to support the indemnification obligations assumed under the separate agreement “Investigator Agreement – Study No. CAN-PRO-NEPA-001 Responsibilities and Procedures”.

## **15 USE OF INFORMATION AND PUBLICATION**

Details concerning the procedures to be followed prior to publication are outlined in a separate agreement “Investigator Agreement – Study No. CAN-PRO-NEPA-001 Responsibilities and Procedures”.

Prior to study start, the study will be published in a public study register. The summary of the results and/or the final medical report will be published in a publicly-accessible database no later than one year after study completion (LPO) and may be presented at a scientific congress.

## **17 APPENDICES**

**Appendix 1: Subject Information and Informed Consent Form**

**Appendix 2: Patient Diary**

**Appendix 3: FLIE questionnaire**

**Appendix 4: WPAI-NV questionnaire**

**Appendix 5: HEC and MEC Emetogenicity**

**Appendix 6: Safety Reporting Forms**

**Appendix 7: Pregnancy Notification Form**

**Appendix 8: Study Drug Access Card**

## Appendix 2: Patient Diary

Dear patient,

This booklet contains a diary which you should complete daily during your participation in this study. The patient daily diary will be used to capture the nausea and vomiting you experienced, the medication for the treatment of nausea and/or vomiting you took and to assess the effectiveness of the study treatment in controlling nausea and vomiting. The diary will be collected during study visits and reviewed with you by study personnel.

Please read the instructions carefully before filling the diary. If you have any questions regarding the diary, please contact study personnel.

There are no right or wrong answers. All information you provide will be strictly confidential.

Thank you for your participation in this study.

---

### GENERAL INSTRUCTIONS

- Please bring back the diary at each study visit.
- Please make sure that all writing is clear and readable.
- If you make a mistake, cross it out and make your change readable. Please do not use liquid paper or white out to make your changes.
- Please record the dates and times in the following format:

Date: dd/mmm/yyyy (i.e., 12/Mar/2018)

Hour: hh:mm (24-hour clock) (i.e., 18:45)

- Please complete all questions. Do not leave blank spaces.

### NAUSEA

To help assess how good or bad your nausea is, we have drawn a scale which ranges from 0 (no nausea) to 100 (nausea as bad as it could be). Each day, for the first 5 days following chemotherapy, we would like you to indicate on this scale how good or bad your nausea was, in your opinion. Please draw a straight vertical line on the scale to indicate how good or bad your nausea was each day. Please see an example below.

CAN-PRO-NEPA-001	PATIENT DIARY DAILY EVALUATION	   -    - 
		Site Number      Patient Number      Cycle #

DAY 1 EVALUATION: 0 - 24 HOURS AFTER START OF CHEMOTHERAPY				
Please complete the page on: <small>(for study personnel only)</small>	  /	   /	   	  :  
	<small>dd</small>	<small>mmm</small>	<small>yyyy</small>	<small>hh</small> : <small>mm</small>

Please remember to record any experience of retching (unproductive vomiting) and/or vomiting on pages 12 to 13 and the medication(s) you took for the treatment of nausea and/or vomiting on pages 14 to 15.

Please evaluate your severity of nausea for the 0 to 24-hour interval after the start of chemotherapy.

Example: Start of chemotherapy – 01June2018 @ 08:00  
 Period of evaluation = 01June2018 @ 08:00 to 02June2018 @ 07:59

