## 2.2 Secondary Outcomes

The response to Akynzeo® and the necessity for use of a rescue medication will be recorded to evaluate effectiveness. The medicinal products used as rescue medication will also be recorded. The following parameters will be calculated from information recorded in the patient diary:

- Complete Response (CR): no emetic episode and no use of rescue medication in the overall period (0-120h/Day 1-5)
- Severity of nausea (daily from Day 1 to Day 5) using a VAS scale (Visual Analogue Scale)
- Time to failure (time to first emetic episode or time to rescue)
- Use of rescue medication (daily from Day 1 to Day 5)

The collection of safety data and adverse events AEs in connection with administration of Akynzeo® will be performed.

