### 3.5 Secondary Endpoints

The secondary endpoints are:

- FLIE total score cycles 2-4
- FLIE Nausea domain total score all cycles
- FLIE Vomiting domain total score all cycles
- Complete response-no emesis, no rescue medication during the acute, delayed and overall phase all cycles
- No significant nausea during the acute, delayed and overall phase for all cycles
- Time to failure defined as time to first emetic episode or time to rescue medication use for all cycles
- Use of rescue medication all cycles
- To descriptively assess the patient diary at screening and over time

The response to Akynzeo® and the necessity for use of a rescue medication will be recorded to evaluate effectiveness. Any medicinal products used as rescue medication will be recorded in the patient diary.

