### 7.2 Sample Size Determination

The study is to include up to 200 patients. No formal sample size calculation has been carried out. The planned number of patients to be enrolled in the study should be adequate for the exploratory purposes and allow a conclusion to be drawn regarding the use of Akynzeo® in real life in Canada.

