**1. NAUSEA**

How much nausea did you experience on average during the last 24 hours?

Please mark on the following scale with a straight vertical line:

 No nausea 0 mm	 Always severe nausea 100 mm	Nausea (for study personnel only)    mm
--------------------------------------------------------------------------------------------------------	---------------------------------------------------------------------------------------------------------------------	-----------------------------------------------------------------------------------------------------------

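### The diary explains the nausea scale with one upper anchor and rating task, but the line patients mark uses another, which adds avoidable error to a secondary outcome

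*Combined protocol and SAP*

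**What the plan says.** Appendix 2 (Patient Diary) describes the nausea scale twice.

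- **Instruction page (NAUSEA).** It tells the patient that "we have drawn a scale which ranges from 0 (no nausea) to 100 (nausea as bad as it could be". The task is given as "Please draw a straight vertical line on the scale to indicate how good or bad your nausea was each day". Averaging is not mentioned. The page refers to a worked example, which is not visible in the text available for review.
- **Daily pages, Days 1 to 5, item 1.** The Day 1 line is labelled "Always severe nausea 100 mm" at its upper end, and the other four days carry the same wording. The question above it is "How much nausea did you experience on average during the last 24 hours". Study personnel then record the mark in millimetres.

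The lower anchor is the same in both places. Nothing in the protocol or diary says how the two upper anchors relate.

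Section 2.2 lists as a secondary outcome "Severity of nausea (daily from Day 1 to Day 5) using a VAS scale (Visual Analogue Scale", and Section 6.7 repeats it as a diary parameter. Section 3.5 adds the endpoint "No significant nausea during the acute, delayed and overall phase for all cycles", with no millimetre cut-off and no stated source. The primary endpoint (Section 3.4) is the FLIE total score for cycle 1.

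**The concern.** The two upper anchors describe different things. The instruction page sets a maximum of intensity. The daily pages combine persistence (always) with a grade (severe) that need not be the worst imaginable. A patient with severe but not worst-possible nausea all day has reached the end of one scale and not of the other. The task shifts as well, from a general judgement of the day to a 24-hour average.

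The diary asks patients to read the instructions carefully before filling it in, so both definitions will be seen. Some patients may carry the first to the line and others may follow the printed label. Marks of the same length would then mean different things in different patients. This visual analogue scale (VAS) is the study's daily measure of nausea severity, and the FLIE nausea items look back over five days, so they cannot replace it. The study is a single cohort with descriptive analyses (Section 7.3), so there is no comparison arm in which the same error would offset. If a cut-off for significant nausea is later applied to this line, marks near it could fall on either side depending on which anchor the patient used.

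**Working it through.** **No plan figure to reproduce.** Section 7.2 states "No formal sample size calculation has been carried out", and no standard deviation, effect size or VAS threshold is given. The check is a comparison of the wording, followed by an illustration under stated assumptions.

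**Wording side by side**

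| | Instruction page | Daily pages 1 to 5 |
|---|---|---|
| Lower anchor | no nausea | no nausea |
| Upper anchor | worst possible intensity | always severe |
| Task | how good or bad, each day | average over 24 hours |

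The difference recurs on every daily page, so it is not an isolated misprint or a PDF-reading fault.

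**Illustration.** Assumed inputs, none of them from the documents: nausea of intensity *I* (0 to 100 on the worst-possible scale), counted as severe, lasts *h* hours of the 24, with none otherwise.

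- Mark under the instruction anchor, averaged over the day: *I* × *h*/24.
- Mark under the daily-page anchor, read as the share of the day with severe nausea: 100 × *h*/24.
- Gap due to the anchors alone: (100 − *I*) × *h*/24.

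*Sustained severe nausea, h = 24, I = 70 to 85*
- *I* = 70: 70 mm against 100 mm, gap (100 − 70) × 24/24 = 30 mm.
- *I* = 85: 85 mm against 100 mm, gap (100 − 85) × 24/24 = 15 mm.

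*Brief episodes, h = 2 to 6, I = 70 to 100*
- *h* = 2, *I* = 70: 5.8 against 8.3 mm, gap 2.5 mm.
- *h* = 6, *I* = 70: 17.5 against 25.0 mm, gap 7.5 mm.
- *I* = 100, any *h*: gap 0 mm.

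With averaging under both anchors, the gap is therefore about 15 to 30 mm for sustained severe nausea and about 0 to 7.5 mm for brief episodes.

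**If the averaging instruction is not followed.** A patient who rates the peak marks *I* itself. For 2 to 6 hours at intensity 70 to 100, the difference from the share-of-time mark runs from 70 − 25 = 45 mm (*h* = 6, *I* = 70) to 100 − 8.3 = 91.7 mm (*h* = 2, *I* = 100). That contrast is between peak and average and does not measure the effect of the anchors.

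**The case against.** The strongest reply is that the line actually marked and measured is consistent. All five daily pages carry the same question, anchors and millimetre labels, and the only form shown has a cycle field. The mismatch is confined to the introductory page. Kit education before chemotherapy (Table 1 footnote, Section 6.1) and diary review at visits may lead patients to the printed label, and the unseen worked example may already show it. The study is descriptive and the primary endpoint does not use this line.

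Much of this stands, and it limits the point in four ways.

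- A reader might infer very large shifts, for example that four hours of worst-possible nausea could be marked near 17 mm or near 100 mm. The documents do not support attributing that to the anchors. Following the daily question, such a day averages 4/24 × 100, about 17 mm, under either anchor. Reaching 100 mm means rating the peak against the printed question.
- A reader might infer drift from day to day in the same patient. The identical daily pages give no textual basis for this. Differences between patients are the plausible form of the error.
- A reader might infer that this line is the sole source for the endpoint of no significant nausea. Section 3.5 names no source, and the diary also holds graded appetite items and a question on medication for severe nausea. Derivation from the VAS is likely but unstated.
- A reader might say that patients are trained on the discordant anchor. No training content is shown.

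What the reply does not remove is the contradiction itself. Patients are given two definitions of the upper end, and no text tells them which governs.

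**Conclusion.** The point holds as a minor defect in a patient-facing instrument. The instructions and the marked line define the upper end of the nausea scale differently and set different rating tasks, which allows avoidable between-patient error in the secondary outcome of daily nausea severity. The endpoint of no significant nausea is affected only if it is derived from this line. The primary endpoint is untouched, and no sample size or power figure depends on the point.

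The size is an illustration. The 15 to 30 mm range rests on the assumption that sustained severe nausea sits at 70 to 85 on the worst-possible scale. The 0 to 7.5 mm range rests on episodes of 2 to 6 hours at 70 to 100, averaged under both anchors. The share of patients who would use the instruction-page anchor is unknown, so the effect on group summaries cannot be estimated from the documents.

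**What to change.** Reword the sentences on the instruction page that define the scale and the task, so that they use the upper anchor printed on the daily pages and ask for the average over the last 24 hours. Check the worked example and change it only if its anchor differs. Leave the five daily lines as they are: they are the measured scale, and changing them instead would mean editing five pages and, if any diaries were already completed, mixing two scales in one dataset.

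If diaries with the present instructions are already in use, the SAP, which Section 7.3 places before database lock, should name the daily-page anchor as the scale that was measured and record the mismatch as a limitation. If the endpoint of no significant nausea is taken from this line, its cut-off should be stated on that same scale.

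The cost is a diary edit of about one sentence, distributed to up to 20 sites (Section 3.2). Under Section 11.1, updated written material for subjects needs REB review and approval, so notification alone would not be enough. No visit, endpoint or data field changes.

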**1. NAUSEA**

How much nausea did you experience on average during the last 24 hours?

Please mark on the following scale with a straight vertical line:

 No nausea 0 mm	 Always severe nausea 100 mm	Nausea (for study personnel only)    mm
--------------------------------------------------------------------------------------------------------	---------------------------------------------------------------------------------------------------------------------	-----------------------------------------------------------------------------------------------------------

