EXCLUSION CRITERIA (as per Contraindications in the approved Canadian Product Monograph)	
 
• Women of child bearing potential who are pregnant, planning on becoming pregnant or breast feeding.
 
• Hypersensitivity to active substances, excipients or other ingredients of Akynzeo®.
 
• Concomitant use of pimozone, terfenadine, astemizole, or cisapride.
 
• Patient is enrolled in another clinical trial where antiemetic treatment is pre-specified by the study protocol.
 

---

STUDY DURATION	This study will last approximately 20 months from 1 st patient enrolled until last patient has completed. The observation period for each subject will last 4-6 months.
RECRUITMENT PERIOD	Approximately 12 months
ANALYSIS	Descriptive statistics will be generated for the primary, secondary and exploratory endpoints.

Table 1: Time and event schedule

Activity	Screening/ Visit 1	Visit 2 Cycle 1	Visit 3 Cycle 2	Visit 4 Cycle 3	Visit 5 Cycle 4	Visit 6/Final visit
Time period	-28 days to Day 1, Cycle 1	Day 1 of Cycle 1	Day 1 of Cycle 2	Day 1 of Cycle 3	Day 1 of Cycle 4	Within 28 days of Cycle 4 or prior to start of next chemotherapy cycle
Informed consent	X					
Inclusion/Exclusion	X					
Demographics & Medical History	X					
Nausea assessment - physician	X					
Current treatments/medications	X					
Patient Kit (distribute and provide education on use)	X*					
Patient Assessments:						
Patient diary, including: 
 
• Nausea Severity Assessment
 
• Rescue medications
 
• Adverse Events
 
		X 	X 	X 	X 	
• Functional Living Index – Emesis (FLIE)		X 	X 	X 	X 	
• Work Productivity Activity Impairment Scale – Nausea and Vomiting (WPAI-NV)		X 	X 	X 	X 	
Patient Kit - collect and review diary and questionnaires			X	X	X	X
Concomitant medication		X	X	X	X	X
Adverse event		X	X	X	X	X
Study completion assessment/early discontinuation						X

\*Patient Kit can be distributed at Screening/Visit 1 or Visit 2. All assessments/training should be completed prior to chemotherapy treatment

 Patient completes diary on days 1-5 (0-120 hours) post chemotherapy cycle

 Patient completes FLIE and WPAI after day 5 of cycle

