### 6.2 Visit 2 (1st Day of cycle 1)

- Akynzeo® taken by patient one hour prior to chemotherapy administration
- Diary completed days 1-5 (0-120 hours post chemotherapy administration)
  - Day 1 is defined as a 24-hour period starting at the time chemotherapy is administered (0-24 hours)
  - Day 2 is defined as 25-48 hours after start of chemotherapy
  - Day 3 is defined as 49-72 hours after start of chemotherapy
  - Day 4 is defined as 73-96 hours after start of chemotherapy
  - Day 5 is defined as 97-120 hours after start of chemotherapy
- FLIE is completed after the end of Day 5/120 hours after start of chemotherapy administration
- WPAI-NV completion is completed after the end of Day 5/120 hours after start of chemotherapy administration
- Assessment of adverse events
- Assessment of concomitant medications

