**2. Have you experienced any vomiting in the last 24 hours?**

- No
- Yes → Please record on the Retching and/or Vomiting page (page 12).

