**4. Did you take any medications because of severe nausea?**

- No
- Yes → Please record on the Rescue Medication page (page 14).

CAN-PRO-NEPA-001	PATIENT DIARY	
 
  	 	 	-	 	 	 	-	 	
 
 Site Number		Patient Number		Cycle #	
 
				-				-		Site Number				Patient Number				Cycle #
					-				-											
Site Number				Patient Number				Cycle #												
	DAILY EVALUATION																			

DAY 2 EVALUATION: >24 - 48 HOURS AFTER START OF CHEMOTHERAPY																													
Please complete the page on: (for study personnel only)	
 
  	 	/	 	 	 	/	 	 	 	 	:	 	 	
 
 dd		mmm		yyyy		hh	mm	
 
			/				/					:			dd			mmm				yyyy					hh	mm
		/				/					:																		
dd			mmm				yyyy					hh	mm																

Please remember to record any experience of retching (unproductive vomiting) and/or vomiting on pages 12 to 13 and the medication(s) you took for the treatment of nausea and/or vomiting on pages 14 to 15.

Please evaluate your severity of nausea for the >24 to 48-hour interval after the start of chemotherapy.

Example: Start of chemotherapy – 01June2018 @ 08:00  
 Period of evaluation = 02June2018 @ 08:00 to 03June2018 @ 07:59

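### The diary's nausea item looks back 24 hours from completion while the page fixes an interval from chemotherapy start, so an off-schedule page can rate the wrong hours

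*Combined protocol and SAP*

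**What the plan says.** Each daily page in Appendix 2 describes the period to be rated in two ways.

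- **Fixed interval.** The Day 1 page instructs: "Please evaluate your severity of nausea for the 0 to 24-hour interval after the start of chemotherapy". Its worked example reads "Period of evaluation = 01June2018 @ 08:00 to 02June2018 @ 07:59". The Day 2 page says "Please evaluate your severity of nausea for the >24 to 48-hour interval after the start of chemotherapy", and Days 3 to 5 follow the same pattern. Section 6.2 defines Days 1 to 5 by the same 24-hour blocks from chemotherapy.
- **Look-back window.** Item 1, answered with a mark on the visual analogue scale (VAS), asks "How much nausea did you experience on average during the last 24 hours". Item 2 asks "Have you experienced any vomiting in the last 24 hours". Both wordings recur on all five pages.

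Each page has a date and time box, "Please complete the page on", marked for study personnel. It shows when the page is due. The page text has no entry for when the patient actually filled it in. Retching, vomiting and rescue medication go into separate logs with dates and clock times.

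Section 3.5 lists absence of significant nausea, by phase and for every cycle, as a secondary endpoint. Section 2.2 lists daily nausea severity.

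**The concern.** The analysis treats the Day 1 rating as nausea in the first 24 hours and the later ratings as delayed-phase nausea. A patient who takes item 1 literally rates whatever 24 hours preceded the pen mark. The VAS is one untimed average per page, so an off-time answer cannot be recognised or moved afterwards. The rule in section 7.3 that excludes implausible or ambiguous data does not help, because nothing marks such a rating as ambiguous.

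Off-time completion is easy to imagine. Section 6.8.2 has the patient complete the diary daily from the day of chemotherapy, yet the Day 1 interval closes only on the following day. A patient who fills in each page on the evening of its calendar day would be early on every page.

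At stake are the daily nausea scores and the acute/delayed split of the nausea endpoint. The acute phase is the more exposed, since it rests on a single page.

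**Working it through.** The plan gives no figure to reproduce. The check is how far the two windows overlap.

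**Inputs.** Page intervals come from Appendix 2 and section 6.2: Day k covers hours 24(k−1) to 24k after the start of chemotherapy. Section 1.1 puts the acute/delayed boundary at 24 h and the end of the delayed phase at 120 h. The shift s is the completion time minus the time the interval closes. The documents give no completion-time data, so s = ±3, ±6 and ±12 h are assumptions.

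**Formula.** A literal answer covers hours 24(k−1)+s to 24k+s. For |s| up to 24 h, the share outside the page's interval is |s|/24.

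| Shift (h) | Share outside | Share inside |
|---|---|---|
| 3 | 3/24 = 12.5% | 87.5% |
| 6 | 6/24 = 25% | 75% |
| 12 | 12/24 = 50% | 50% |

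**Where the stray hours fall, for a 6 h shift.**

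| Page | Early by 6 h | Late by 6 h |
|---|---|---|
| Day 1 | −6 to 18: 6 h before chemotherapy, 6 acute hours missed | 6 to 30: 6 h delayed counted as acute |
| Day 2 | 18 to 42: 6 h acute counted as delayed | 30 to 54: all delayed |
| Day 3 | 42 to 66: all delayed | 54 to 78: all delayed |
| Day 4 | 66 to 90: all delayed | 78 to 102: all delayed |
| Day 5 | 90 to 114: all delayed | 102 to 126: 6 h beyond 120 h |

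The pattern is the same at 3 and 12 h. Of ten combinations, two mix acute and delayed time (Day 1 late, Day 2 early), two bring in time outside both phases (Day 1 early, Day 5 late), and six change the day but not the phase.

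**Evening completion, with assumed times.** Chemotherapy starts at 10:00 and pages are filled in at 20:00. The Day 1 page, completed 10 h after the start, has s = 10 − 24 = −14 and covers hours −14 to 10: 14/24 = 58.3% lies before chemotherapy. The Day 2 page, completed at 34 h, has s = 34 − 48 = −14 and covers hours 10 to 34: 14/24 = 58.3% is acute time counted as delayed.

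**After rewording.** If the item names the page's own interval, the share outside is 0% at any completion time. Ordinary recall error remains.

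**The case against.** The page itself does much to prevent the error. The interval heading, the explicit instruction, the clock example and the scheduled time all stand above the question, patients are trained on the kit, and staff review the diary with them. Error requires two things together: off-time completion, and a patient who follows the item rather than the instruction. That stands, and it is why the wording *can* misplace nausea; the documents do not show that it will.

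A reader might infer more than the documents support, in four ways:

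- *Any mistimed page puts nausea in the wrong phase.* It does not. Acute and delayed time mix only at the Day 1/Day 2 boundary.
- *The vomiting results are equally exposed.* Item 2 only directs the patient to a log that covers the full 120 hours and takes the date, onset and end time of each episode. Rescue intake is timed as well. Complete response and time to failure can be derived from these logs.
- *Due times are unreliable throughout because the kit may be issued up to 28 days before chemotherapy.* Table 1 does say "Patient Kit can be distributed at Screening/Visit 1 or Visit 2", but nothing says that staff fill in the due time when they hand out the kit. Sections 6.3 to 6.5 distribute the diaries for cycles 2 to 4 on Day 1 of each cycle, so this concerns cycle 1 at most.
- *The percentages measure bias.* They measure window overlap under a fully literal reading.

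The affected measures are also secondary, and section 7.3 makes all analyses descriptive. That limits the weight of the point. It does not remove a contradiction printed on every daily page.

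**Conclusion.** The point holds in limited form: items 1 and 2 contradict the interval printed on their own page and section 6.2, and for the nausea VAS an off-time literal answer can be neither detected nor reassigned. The share of the window asked about that falls outside the interval is 12.5%, 25% or 50% at assumed shifts of 3, 6 or 12 h. How often pages are mistimed, how many patients would follow the item, and the resulting effect on mean scores or on the nausea endpoint cannot be worked out from the documents.

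The exposure is confined to daily nausea severity and the acute/delayed split of the nausea endpoint, plus time outside the phases on an early Day 1 or late Day 5 page. The primary endpoint, FLIE total score in cycle 1, does not use this item. This is a cheap improvement to a secondary measure, not a threat to the study's main result.

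**What to change.** 1. On each page, replace the look-back in item 1 with that page's own interval; for Day 1, for example, *during the 0 to 24 hours after the start of your chemotherapy*. Change item 2 in the same way for consistency.
2. Have staff or the patient write the actual start date and time in the diary once chemotherapy has begun. This should not be done at screening, nor at the chemotherapy-day visit itself: section 3.1 places Visits 2 to 5 before administration, so the actual start may not yet be known.
3. Add a completion date and time, entered by the patient, to each page so that off-time ratings can be identified.

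The cost is reprinted diary pages and REB review and approval, since section 11.1 requires this for updates to written material given to subjects. No visits, patients or procedures are added, and no sample size or error rate changes.
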